In this sense, some studies are being conducted on the use of mobile technology to control hypertension, aiming at greater access to the patient, education and awareness of the disease, as well as the patient's engagement in their care [29,30,31,32,33]. In a previously developed study, it was seen that virtual distance or face-to-face teaching, through "e-learning", helps to reduce the effect of the white coat and the anxiety of hypertensive patients, with an improvement in adherence to treatment [34].

However, it is not yet known the best technological tools to help hypertensive patients to improve treatment adhering to healthy life habits and, and consequently avoid the complications of AH. In addition, this tool needs to be feasible to be used by patients or caregivers, regardless of social class, preserving their intimacy, privacy and still obtaining the desired health improvement results.

Based on these arguments, the hypothesis of the proposal is that the use of an application developed by artificial intelligence adapted to individual needs and customs can help improve therapeutic adherence and provide better BP control in patients with uncontrolled hypertension.

2. Primary objective

To evaluate the effectiveness of an artificial intelligence application developed for home monitoring compared to institutional standard follow-up in patients with uncontrolled hypertension in the following parameters:

- a) To obtain adequate control of blood pressure (< 140/90 mmHg) of the office and of the blood pressure ambulatory monitoring (< 135/85 mmHg at wakefulness)
- b) Improving adherence to drug treatment assessed by a validated questionnaire

- c) Reduce dietary sodium intake and 24-hour urinary sodium
- d) Increase the performance of physical activity evaluated by number of daily steps
- e) Reduction of body weight and abdominal circumference

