3.1. Study design

Randomized study with patients with uncontrolled hypertension followed at the Outpatient Clinic of the Hypertension Unit of the Heart Institute (InCor-HCFMUSP), for the use of an application for monitoring and engagement to antihypertensive treatment - compared to the standard follow-up of the institution in a 12-month follow-up.

The study involves the direct participation of an institutional multidisciplinary team with an international partnership and a national institution of advanced technology in artificial intelligence. The hospital's team includes physicians, nurses, nutritionists, psychologists, physical educators and biomedical, supported by the institution's own innovation team. The international team includes all members of the Inavya Ventures LTd.

Will be included 100 patients diagnosed with primary arterial hypertension under drug treatment, with at least 3 classes of antihypertensive drugs in an optimized dose, aged 20 to 65 years, and who present clinic BP ≥ 140 and/or 90 mmHg, and wakefulness BP in ambulatory BP monitoring $\geq 135/85$ mmHg. Patients or their caregivers should also be able to use mobile phones and apps.

Patients with stroke sequelae or those with significant cognitive dysfunction will be excluded.

Randomization will be done in the 1:1 form using electronic randomization system, without knowledge by the team involved in the study. There will be two groups in the project,

so that, patients will be randomized to intervention group (application use) or control group (standard follow-up of the institution).

In the intervention group (N= 50), patients will receive a cellular device (by donation consigned by a telephone company) for the exclusive use of the application within 12 months. In this mobile device will be installed, with the guidance of the multidisciplinary team, the AVATR application developed in partnership with the company Inavya Ventures Ltd., where they will be digitized with individualized code for each patient, personal data, including age, gender, behavioral patterns and lifestyle habits (walks, type of diet, quality of sleep, etc.), and daily medications used.

The data will be allocated in a dedicated cloud and protected by cutting edge encryption. All this part of data capture and storage is in accordance with the rules of the General Data Protection Law (GDPL) as well as the General Data Protection Regulation (GDPR), the uk regulation.

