3.12. Statistical analysis

All analyses will be performed based on the complete population of the set of analyses, and all values of the clinic BP and the mean wakefulness of the ABPM will be included. The

characteristics of the patient at the initial visit will be described using mean \pm standard deviation or median deviation (quartiles) for continuous variables, or number (proportion in %) for categorical variables. To compare the main variables before and after using the application, the appropriate tests will be performed according to the type of the variable, that is, whether quantitative or qualitative. Thus, to compare the quantitative variables (blood pressure value, weight, body mass index, abdominal circumference, 24-hour urine sodium and questionnaire score), a comparative analysis of a paired t-test will be performed. For the nonparametric variables, the chi-square and kruskall wallis test will be used to compare them.

4. Expected results

The use of the artificial intelligence application for distance monitoring of patients with uncontrolled hypertension should provide greater engagement of patients and their families in treatment, and thus may lead to better blood pressure control, greater adhering to healthy lifestyle habits (decreased sodium intake, increased physical activity and improved quality of life) when compared to the follow-up currently performed at the institution. Better blood pressure control of these patients, who generally require a high number of medications, may consequently reduce the risks of complications and also the search for emergency services, which can harm the patient, and also encumber the health service. In addition, the integrated participation of a multidisciplinary team more actively ensures greater involvement with patient care, without the need for frequent returns to the Unit for better blood pressure control.

5. Timeline

Month	Activity
1st to 2nd month	Selection of participants
2nd to 3rd month	Signature of the GDPL and training of patients with application
5th to 6th month	Consultation for data collection and delivery of the blood pressure measurement device
7th to 12th month	Monitoring patients by staff through the application
7th to 12th month	Consultation for data collection and delivery of the blood pressure measurement device

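### Section 3.12 gives the listed quantitative outcomes a paired before/after t-test and no between-arm test, so the stated analysis does not answer the randomised question

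*Protocol*

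**What the plan says.** Section 3.12 opens its account of the tests with "To compare the main variables before and after using the application, the appropriate tests will be performed". For the quantitative variables (blood pressure value, weight, BMI, abdominal circumference, 24-hour urinary sodium, questionnaire score) it states that "a comparative analysis of a paired t-test will be performed". The only other rule is "For the nonparametric variables, the chi-square and kruskall wallis test will be used to compare them", and it does not say which groups are compared.

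The rest of the protocol asks a between-arm question:

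- Section 2 gives the main aim in these words: "To evaluate the effectiveness of an artificial intelligence application developed for home monitoring compared to institutional standard follow-up in patients with uncontrolled hypertension". Item (a) is a threshold outcome, "To obtain adequate control of blood pressure (< 140/90 mmHg) of the office", together with an awake ambulatory threshold.
- Section 3.1: "Randomization will be done in the 1:1 form using electronic randomization system", with 50 patients per arm.
- Section 4 expects benefit "when compared to the follow-up currently performed at the institution".

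Section 3.1 also says that controls have the same initial evaluation, receive lifestyle guidance then, and have it reinforced at clinic visits. In the application arm, the initial evaluation comes after a 15-day period of getting used to the application.

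**The concern.** A paired t-test contrasts two measurements on the same patient. It cannot contrast two independent groups. Controls never use the application, so a comparison defined by its use does not, read literally, include them. The listed variables carry most of the primary objective: blood pressure, adherence score, urinary sodium, weight and abdominal circumference. Followed as written, the analysis would collect control data and leave them out of the stated test.

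A shared fall is plausible from the protocol's own design. Patients enter because their clinic and awake ambulatory pressures are high, so some regression towards the mean is expected, most of all if the qualifying readings serve as the starting value. Both arms also receive guidance and a year of specialist follow-up.

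A second, smaller problem concerns the starting value. In the application arm, visit 1 follows 15 days of use, so any early effect is already in it and drops out of the before/after change.

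**Working it through.** The protocol states no alpha, SD, expected change or power, so there is no figure of its own to reproduce. The defect shows from the text; the numbers below only indicate its size.

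**Inputs.** From the protocol: n = 50 per arm. Assumed: two-sided alpha 0.05; SD of change in systolic pressure 12, 15 or 18 mmHg; the same true fall d of 2, 3 or 4 mmHg in both arms, so the true application effect is zero.

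**Step 1: paired test in application users.** The noncentrality is d/SD × √50 on 49 degrees of freedom. For d = 3 and SD = 15 it is 0.2 × 7.07 = 1.41, and the probability of significance is 0.284.

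**Step 2: paired test in each arm, results set side by side.** The arms are independent, so the probability of a significant fall with the application and a non-significant control result is P(significant fall) × (1 − P(significant)). For d = 3 and SD = 15 this is 0.284 × 0.716 = 0.203.

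| SD of change | Step 1, d = 2 / 3 / 4 | Step 2, d = 2 / 3 / 4 |
|---|---|---|
| 12 | 0.212 / 0.410 / 0.637 | 0.166 / 0.242 / 0.231 |
| 15 | 0.152 / 0.284 / 0.456 | 0.127 / 0.203 / 0.248 |
| 18 | 0.120 / 0.212 / 0.338 | 0.103 / 0.166 / 0.224 |

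The Step 2 figure cannot rise much above 25%, because p(1 − p) peaks at p = 0.5. The Step 1 figure has no such ceiling: at SD 15 a shared fall of 5 mmHg gives 64%, and one of 10 mmHg gives over 99%. Pooling both arms in one paired test (n = 100) gives 51% at d = 3 and SD 15, and also says nothing about the difference between arms.

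**Step 3: between-arm test on the same data.** In simulation (50,000 trials per cell) a two-sample t-test on change was significant in 4.8–5.1% of trials, and in 2.4–2.6% in favour of the application. The simulated values for Steps 1 and 2 agreed with the table within 0.004.

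**Step 4: starting value after 15 days of use.** Assume the application has already lowered visit-1 pressure by 2 mmHg, the true 12-month difference is 6 mmHg, and the SD is 15 mmHg at both times with correlation r (equal to the slope here, as the SDs are equal).

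- Before/after change in the application arm: 6 − 2 = 4 mmHg, so all 2 mmHg are lost.
- Between-arm comparison adjusted for visit 1: the expected loss is r × 2, that is 0.8, 1.2 or 1.6 mmHg for r = 0.4, 0.6 or 0.8. Simulation gave 5.17, 4.81 and 4.40 mmHg.
- Unadjusted between-arm comparison at 12 months: no loss (simulated 5.95–6.02 mmHg).

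These correlations imply an SD of change of 15 × √(2(1 − r)) = 16.4, 13.4 and 9.5 mmHg. The r = 0.8 case therefore lies outside the 12–18 range of Steps 1 and 2 and is best read as an outer bound.

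**The case against.** The strongest reply is that section 3.12 never calls the before/after comparison the effectiveness test and does not rule out a between-arm analysis, which an SAP could add. That would carry weight if the protocol were silent. It is not: it names a comparison and a test for these outcomes, and neither fits the objective. An SAP that followed it would inherit the error, and one that departed from it would contradict the protocol.

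Three points stand in part.

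- Chi-square and Kruskal-Wallis ordinarily compare independent groups, so the proportion with controlled pressure in item (a) may well be meant as a between-arm test. For that outcome the fault is only that the grouping is not named. The firm finding is confined to the listed quantitative variables.
- The 15-day point is a separate issue and works the other way, hiding benefit. The home pressure device is handed over only after those 15 days, and nothing in the protocol shows that an early effect exists. It stays conditional, but it matters when choosing what to adjust for.
- The assumed falls and SDs are not anchored in the protocol. They illustrate the size and do not carry the conclusion.

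**Conclusion.** Section 3.12 is wrong as written for the listed quantitative outcomes: the test it fixes does not compare the application with standard follow-up. This must be corrected before analysis. The conclusion rests on the text alone.

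For scale, with no application effect, an SD of change of 12–18 mmHg and shared falls of 2–4 mmHg, the paired test in application users would be significant in 12–64% of trials. Separate tests in each arm would show the misleading pattern in 10–25%. The matching error of a between-arm test is about 2.5%. The starting-value problem depends on an early effect that may not exist; if it were 2 mmHg, the before/after change would miss all of it.

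**What to change.** Reword section 3.12 as follows.

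1. For each quantitative outcome measured in both arms, make the difference between randomised arms at 12 months the effectiveness test, with patients analysed as randomised.
2. Compare the proportion with controlled pressure between arms, and name arm as the grouping factor for chi-square and Kruskal-Wallis.
3. Keep before/after changes within each arm as description only.
4. Adjust for a value recorded before application use where both arms have one. For pressure this means the qualifying clinic and awake ambulatory readings, if they are kept as study data; section 3.1 lists ambulatory monitoring at visits 2, 3 and 5, not at visit 1. Where only the visit-1 value exists, report the adjusted and unadjusted 12-month comparisons together and state in advance which one leads.
5. Daily steps, item (d) ("Increase the performance of physical activity evaluated by number of daily steps"), are not in the section 3.12 list and are described only for the application arm's study phone. Treat them as within-arm description unless controls are measured too.

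The exact model can be left to the SAP.

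The cost is a rewording and slightly more analysis, on data already planned in both arms. Only a between-arm comparison of steps would need new measurement. The sponsor should also know what this comparison can detect. With 50 per arm, two-sided alpha 0.05 and 80% power, the detectable difference in change is SD × √(2/50) × (1.96 + 0.84): 6.7, 8.4 or 11.2 mmHg for an assumed SD of 12, 15 or 20 mmHg, ignoring dropout. The rewording does not create that limit; it is the precision of the comparison the primary objective already calls for.

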3.8. Food consumption questionnaires

Two questionnaires will be applied to assess food consumption. A form of food consumption markers for individuals older than 5 years that is proposed by the Food and Nutrition Surveillance System. This tool aims to identify the frequency of pre-established food consumption in the last 7 days. The questionnaire has only ten items that are easy to understand

and apply. From item 1 to 5 are foods where daily consumption is recommended. Items 6 to 10 are foods that should be consumed eventually or should be avoided. The 24-hour Dietary Recall consists of a complete description of the interviewee's eating habits the day before the interview. The data to be obtained by the instrument is the type of food or preparation, quantity consumed, place and time of the meal. The participant will be asked to describe the part in homemade measures that will later be transformed into grams of the food. Nutritional information will be based on the Brazilian Food Composition Table.³⁷³⁸

3.9. 8-Stage Moriski Green - Adherence Questionnaire

To evaluate treatment adherence, the Eight-Item Morisky Therapeutic Adherence Scale was used, consisting of eight questions regarding the use of medication. The degree of therapeutic adherence will be determined according to the score resulting from the sum of the answers of the MMAS-8 questionnaire: high adherence (8 points), average adherence (6 or 7 points) and low adherence (<6 points).³⁹

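### Primary objective (a) is BP control against standard follow-up, but section 3.12 names only a before-after test on the BP value, which does not answer it

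*Protocol*

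**What the plan says.** Section 2 frames all primary parameters as a comparison of the application with the institution's standard follow-up. Parameter (a) is the attainment of a target: "To obtain adequate control of blood pressure (< 140/90 mmHg) of the office" together with "the blood pressure ambulatory monitoring (< 135/85 mmHg at wakefulness"). Each patient either meets it or does not.

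Section 3.1 admits only patients whose clinic and awake ambulatory pressures are both above target on at least three drug classes. It randomizes 100 patients 1:1. Office pressure is measured at visits 2 to 5 and ambulatory pressure at visits 2, 3 and 5, so both are available at the 12-month visit.

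Section 3.12 describes the comparison as one before and after use of the application. Its plan "to compare the quantitative variables (blood pressure value, weight, body mass index, abdominal circumference, 24-hour urine sodium and questionnaire score") is that "a comparative analysis of a paired t-test will be performed". It then adds: "For the nonparametric variables, the chi-square and kruskall wallis test will be used to compare them". No variable is listed under that last sentence, and BP control is not mentioned anywhere in the section.

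**The concern.** The objective and the analysis differ in two ways: in the variable (control status against BP value) and in the contrast (between arms against before and after). Someone following section 3.12 literally would report a mean within-patient change in pressure. That does not say how many patients reached target, or whether more did so with the application than with standard follow-up.

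In patients uncontrolled on three or more drug classes, mean pressure can fall while few cross the threshold. Section 4 expects better blood pressure control than under current follow-up. With no deciding form named, a lower mean without a gain in control, or a gain in control without a clear change in the mean, could be put forward as success on objective (a).

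**Working it through.** **The protocol's own figures.** It gives 100 patients, 50 per arm, but no alpha, power, effect size, SD or control rate. There is no sample-size figure to reproduce, so the main check is textual.

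| Element | Section 2, parameter (a) | Section 3.12 |
|---|---|---|
| Variable | Target met or not | BP value |
| Contrast | Application v standard follow-up | Before v after |
| Test | None stated | Paired t-test |
| Control status | The stated aim | Not named |

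**Can the chi-square sentence supply the missing test?** Control is a qualitative variable, so a chi-square test may be intended. The sentence does not say so, and the section's only stated contrast is before against after. Applied that way to control, the baseline proportion is essentially 0% by the entry criteria. The proportion can then only stay level or rise, and regression to the mean after selection on high pressure would raise it in both arms. Only a comparison between arms separates the effect of the application from that rise.

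**Does the form matter?** This illustration rests on assumptions not in the protocol: between-arm tests, two-sided 5%, awake systolic pressure only, normal at 12 months, control-arm mean 145, SD 15, true difference 8 mmHg, 50 per arm.

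*Mean.* Standard error = 15 × √(2/50) = 3.0. Power = Φ(8/3.0 − 1.96) = Φ(0.71) = 0.76 by the normal approximation. A simulated t-test gives 0.75.

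*Proportion below 135.*
- Control arm: Φ((135 − 145)/15) = Φ(−0.667) = 0.2525.
- Intervention arm: Φ((135 − 137)/15) = Φ(−0.133) = 0.4470.
- Difference 0.1945; pooled proportion 0.350.
- Standard error under no difference: √(0.350 × 0.650 × 2/50) = 0.0954.
- Standard error under the alternative: √((0.2525 × 0.7475 + 0.4470 × 0.5530)/50) = 0.0934.
- Power = Φ((0.1945 − 1.96 × 0.0954)/0.0934) = Φ(0.08) = 0.53.

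*Both tests on the same data.* In 20,000 simulated trials of this scenario, the two forms gave different significance verdicts in 27%. With control mean 140 to 150, SD 12 to 18 and a true difference of 5 or 8 mmHg, they disagreed in 17% to 34%. A second set of assumptions (threshold 140, mean 145 or 150, SD 15 or 20, difference 5 to 10 mmHg) gave about 20% to 27%.

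**The case against.** The strongest reply is that section 3.12 first says tests will follow the type of variable, quantitative or qualitative, and then names chi-square. Under that rule a yes/no control status goes to chi-square, and assigning tests to variables is ordinary work for a statistical analysis plan. Part of this stands: the protocol does not exclude a categorical test, and it would be wrong to say that it offers none. But the rule does not name control, does not set it above the BP value that is named, and does not supply a between-arm contrast. The mismatch lies between two statements in the protocol itself, so a later plan would have to depart from one of them or choose between them.

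It can also be said that ranking the primary parameters (a) to (e) would settle this. It would only if the ranking also fixed the form. Making awake pressure the sole primary outcome still leaves value or proportion open.

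Three stronger readings are tempting but not supported:

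- **Adherence has the same fault.** Section 3.9 grades the score as "high adherence (8 points), average adherence (6 or 7 points) and low adherence (<6 points"), so a reader might infer two rival forms here too. But the objective, "Improving adherence to drug treatment assessed by a validated questionnaire", sets no class target, and section 3.12 already names the questionnaire score. The bands describe the instrument and do not create a second deciding test.
- **The false-positive rate is inflated.** If significance on either form counted as success, the simulated rate with no true effect would be 7.4% to 8.8% rather than 5%. The protocol states no such rule, so this is not an error rate of the plan.
- **The disagreement rate is an error rate.** The 17% to 34% largely reflects power lost by dichotomizing, and would arise in any trial that tested both forms.

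**Conclusion.** The point holds for blood pressure only. Objective (a) asks whether more patients reach target with the application than with standard follow-up. The analysis named for blood pressure is a within-patient change in the value. Control status is left to a generic sentence with no variable and no between-arm contrast, and the entry criteria make a before-after test of it uninformative. This conclusion comes from the text and depends on no assumed number.

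The figures show only that the choice of form has consequences: 53% against 75% power in the worked case, and different verdicts in 17% to 34% of simulated trials. They assume between-arm tests that section 3.12 does not specify, and they use awake systolic pressure alone. The full target also includes office and diastolic limits, so fewer patients would meet it than in the illustration.

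This is a worthwhile and inexpensive correction. It does not show that the trial's data could not answer the objective.

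**What to change.** In section 3.12, name the deciding test for objective (a): the between-arm comparison of the proportion of patients controlled at visit 5 (12 months), by the objective's own thresholds of office <140/90 and awake ambulatory <135/85 mmHg. Report the between-arm differences in office and awake BP values at that visit as supportive estimates with confidence intervals.

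This keeps the stated objective and uses measurements already scheduled. It costs a few sentences and no new patients or visits. The real cost is power, about 53% against 75% in the illustrative case, and a BP-value result can then no longer carry the claim on objective (a).

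The opposite choice, letting mean awake systolic pressure decide, would recover that power. It would also mean rewording the primary objective from control to reduction and dropping office and diastolic pressure from the decision. That is a larger change and a debatable trade-off, and this finding does not require it. Nothing needs to change for adherence on this account.

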The control group (N= 50) will perform the same initial evaluation and answer the same questionnaires as described above for the intervention group. In this evaluation will receive guidance regarding the adoption of life habits by the multidisciplinary team. The control group will receive reinforcement of guidance only in clinic face-to-face visits.

The visits of the study after the patient's inclusion will take place every 12 weeks (Visits 2, 3, 4 and 5), totaling 4 visits after the initial visit, with the final visit after 12 months. Patients will perform 24-hour ambulatory blood pressure monitoring (ABPM) at visits 2, 3 and 5. In visits 2 to 5, the patient will have the measurement of blood pressure from the office, weight and abdominal circumference, and data on symptoms and events that occurred (hospitalizations, emergency room visits, symptoms) will be collected. In the last visit (12-month), in addition to these measures, the questionnaires performed on the first visit and laboratory dosages will be repeated.

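### Section 3.12 pairs the quantitative variables but names chi-square and Kruskal-Wallis, which assume independent groups, for the other before/after comparisons; with positive within-patient correlation this makes the tests too conservative.

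*Protocol*

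**What the plan says.** Protocol section 3.12 sets the frame: "To compare the main variables before and after using the application, the appropriate tests will be performed according to the type of the variable". The types it distinguishes are quantitative and qualitative. Quantitative variables (blood pressure value, weight, body mass index, abdominal circumference, 24-hour urine sodium, questionnaire score) follow, and for these "a comparative analysis of a paired t-test will be performed". The next sentence covers the rest: "For the nonparametric variables, the chi-square and kruskall wallis test will be used to compare them". No paired test is named for them, and no comparison of the two randomized groups appears in the section.

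The data are paired. Section 3.1 says that at the 12-month visit "the questionnaires performed on the first visit and laboratory dosages will be repeated".

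Two of the parameters under the primary objective (section 2) have a categorical form. Objective a reads "To obtain adequate control of blood pressure (< 140/90 mmHg) of the office", with a further awake ambulatory threshold. Objective b is adherence, which section 3.9 grades as "high adherence (8 points), average adherence (6 or 7 points) and low adherence (<6 points" on the eight-item scale.

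**The concern.** The paired t-test shows that the authors meant a within-patient comparison. Chi-square and Kruskal-Wallis applied to that comparison treat 50 patients measured twice as 100 unrelated people. Their standard error leaves out the covariance between a patient's two values, so the p-value is wrong whenever that covariance is not zero. Repeated measurements on one patient are usually positively correlated. The true standard error is then smaller than the one the test uses, and real change is harder to detect. In a trial with 50 patients per arm that loss matters.

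This is not a detail left for a later analysis plan. The protocol names the tests, and they do not fit the comparison it names.

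**Working it through.** **Inputs from the protocol.** 100 patients randomized 1:1, so 50 in the application arm (section 3.1). Comparison: before versus after (section 3.12). The protocol gives no significance level, power, effect size or correlation, so there is no stated figure to reproduce.

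**Assumptions.** Two-sided 5% level. High adherence in 30% of patients before and, under change, 50% after. Before/after pairs from a bivariate normal with latent correlation 0.5 or 0.7. Cut at 30% on both occasions, these give binary correlations of 0.32 and 0.48. For continuous variables, correlation 0.3, 0.5 or 0.7 and a shift of 0.4 SD.

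**Step 1: analytic error rate.** With equal variances and correlation r, the variance of the before/after difference is (1 − r) times the value that an independent-groups test uses. A nominal 5% test therefore has true error of about 2 × [1 − Φ(1.96/√(1 − r))].

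- Chi-square, r = 0.32: 1.96/√0.68 = 2.38, error about 1.8%.
- Chi-square, r = 0.48: 1.96/√0.52 = 2.72, error about 0.7%.
- Kruskal-Wallis, using the same approximation, r = 0.3, 0.5, 0.7: about 1.9%, 0.6% and 0.03%.

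**Step 2: simulation, two-level outcome, 50 pairs, 40,000 runs.**

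| Binary correlation | Test | Error, 30% to 30% | Power, 30% to 50% |
|---|---|---|---|
| 0.32 | Chi-square | 1.8-1.9% | 55-56% |
| 0.32 | McNemar, asymptotic | 4.7% | 69% |
| 0.32 | McNemar, exact | 2.7-2.8% | 60-61% |
| 0.48 | Chi-square | 0.7-0.8% | 55-56% |
| 0.48 | McNemar, asymptotic | 4.4% | 79% |
| 0.48 | McNemar, exact | 2.3% | 71-72% |

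Mid-p McNemar lies close to the asymptotic form (power 68% and 79%). Ranges are from repeated runs.

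**Step 3: simulation, ranked outcome, 50 pairs, 10,000 runs.**

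| Correlation | Kruskal-Wallis error | Kruskal-Wallis power | Signed-rank power |
|---|---|---|---|
| 0.3 | about 2% | 49-50% | 63% |
| 0.5 | 0.7-1% | 47-49% | 75-78% |
| 0.7 | 0.1% | 47-49% | 94% |

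The signed-rank test keeps its error near 5% throughout (4.8% to 5.1%).

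**Step 4: can the error run the other way?** Entry requires uncontrolled pressure, so suppose 0 of 50 are controlled before and k of 50 after.

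| k | Chi-square, uncorrected | Chi-square, continuity-corrected | Fisher | McNemar, exact |
|---|---|---|---|---|
| 4 | 0.041 | 0.126 | 0.117 | 0.125 |
| 5 | 0.022 | 0.066 | 0.056 | 0.0625 |
| 6 | 0.012 | 0.035 | 0.027 | 0.031 |

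At k = 4 the smallest expected count is 50 × 4/100 = 2. The corrected and exact independent-samples tests first reach 5% at k = 6, the same point as exact McNemar. Only the uncorrected chi-square differs.

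**The case against.** **The tests may have been meant for application versus control.** There they would be valid, and Kruskal-Wallis with two groups is simply a two-sample rank test. But section 3.12 never mentions that comparison, and its opening phrase governs the sentence. On this reading the sentence still has to be taken out of the before/after frame.

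**The reach is limited.** This stands. Questionnaire score is listed under the paired t-test, as are blood pressure value, weight, body mass index, abdominal circumference and urine sodium. A reader might infer that every skewed score goes to Kruskal-Wallis; the text does not say so, and taking nonparametric variables to mean non-normal ones is an interpretation. What is clearly affected is blood pressure control as yes/no and the adherence degree.

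**The tests might instead produce false positives for blood pressure control.** A reader might infer this from 0/50 versus 4/50, where uncorrected chi-square gives 0.041. The documents do not support it. The result comes from a large-sample approximation with small counts, not from ignored pairing, and section 3.12 does not say that the uncorrected form will be used. If no patient is controlled at baseline, there is also no baseline variation with which to correlate, so the power losses above describe adherence degree better than blood pressure control.

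**The gain depends on the McNemar version.** This also stands. Exact McNemar is itself conservative, and at binary correlation 0.32 it gains only about 5 points over chi-square, against about 14 for the asymptotic form.

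**The larger gap is the absent between-arm comparison.** True, and it is a separate matter. Correct within-arm tests would not answer an objective defined against standard follow-up.

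**Conclusion.** The concern holds as a mismatch between a stated comparison and the tests stated for it. The consequence is conservatism and lost power where within-patient correlation is positive. For a 30% to 50% rise in a two-level outcome, chi-square has about 55% power against 60-79%, depending on correlation and on the McNemar version. For a 0.4 SD shift at correlation 0.5, Kruskal-Wallis has about 47% against 75-78%. At zero correlation the loss disappears. The 5% level, the correlations, the rates and the shift are all assumptions; the misfit itself does not depend on them.

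**What to change.** Replace the final sentence of section 3.12 so that it says:

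- within-arm before/after comparisons use McNemar for two-level variables (naming the exact, mid-p or asymptotic version) and Wilcoxon signed-rank for ordered or non-normal variables;
- chi-square and Kruskal-Wallis (or a two-sample rank test) apply only to comparing the two randomized arms at a given visit, including blood pressure control and adherence degree at month 12;
- within-arm tests are supportive, because they do not address the comparison with standard follow-up.

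The phrase nonparametric variables should give way to a statement of which variables are meant. A proportional-odds model for the month-12 adherence degree, adjusted for baseline degree, would use the ordering of the categories but is optional.

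The cost is a short rewrite of section 3.12 before the data are analysed. It needs no new data, visits or patients.
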